3.5.2 Secondary Outcome Measures

Clinical outcomes

Clinical outcome will include mobility and lower limb function as well as quality of life, self-efficacy skills and goal attainment. This will be collected by an allied health clinician at timepoints (T1), (T2), and an allied health clinician blinded to the previous measures at timepoints (T3) and (T4). The secondary outcome measures and the description of how they will be used is described in Table 1 below:

Table 1: Secondary clinical outcome measures and details of their use in the study

Outcomes with	Description of	How and where	Timepoints when
Outcome Measures	outcome measure	will outcomes be	the outcome will
being used	used	measured	be measured
General Mobility -	The Motor	The MAS will be	(T1) (T3) (T4)
Motor Assessment	Assessment Scale	assessed using the	
Scale (MAS) (22)	for stroke is a	standardised	
	widely used	assessment	
	performance-based	protocol developed	
	scale used to	by Carr and	
	measure 8 different	Shepherd (1985) in	

	domains and 1 item	clinic by the	
	related to muscle	specified allied	
	tone of everyday	health clinician of	
	motor function in	the study at the	
	people with stroke.	noted timepoints	
		•	
	It has a high test-	(22).	
	retest reliability		
	and inter and intra-		
	rater reliability		
	(22).		(= 1) (= 1)
Mobility: Lower	The Short Physical	The SPPB will be	(T1) - (T4)
Limb Function and	Performance	measured using the	
Disability - Short	Battery is typically	standardised	
Physical	used to assess	assessment	
Performance	lower limb function	protocol developed	
Battery (SPPB) (23)	in elderly	by Guralnik and	
	community welling	colleagues (1994)	
	persons. It assesses	in clinic by the	
	balance, gait speed	specified allied	
	and ability to stand	health clinician at	
	from sitting five	the noted	
	times. It has been	timepoints (23).	
	shown to be a		
	predictor of short-		
	term mortality,		
	hospital admission		
	and strongly		
	associated with		
	self-reported		
	disability (23).		
Mobility: Walking	The Two Minute	The 2MWT will be	(T1) - (T4)
Capacity - 2 Minute	Walk Test is a	measured using the	
Walk Test (2MWT)	shortened form of	standardised	
(24)	the 12- and 6-	assessment	
	minute walk tests	protocol developed	
	and is a measure of	by Butland and	
	self-paced walking	colleagues (1982)	
	capacity (24).	in clinic by the	
	- Capacity (2 1).	specified allied	
		health clinician at	
		the noted	
		timepoints (24).	
Quality of Life- 12-	The 12- Item Short	The SF-12 will be	(T1) (T3) (T4)
Item Short Form	Form Survey is a	provided to	(11)(13)(14)
Survey (SF-12) (25)	self-reported	participants by the	
Jul vey (35-12) (23)	measure of the		
		specified allied health clinician at	
	impact of an	Health ChillClaff at	1

	individual's health	the time one inte	
		the timepoints	
	on their daily life	noted in the form it	
	(25).	was developed and	
		no changed made	
		to the content (25).	
Self-Efficacy-	The Exercise Self	The ESES will be	(T1) (T3) (T4)
Exercise Self	Efficacy Scale is a	provided to	
Efficacy Scale	self-reported	participants by the	
(ESES) (26)	measure of	specified allied	
	exercise related	health clinician at	
	self-efficacy and	the timepoints	
	was originally used	noted and in the	
	in people with	form it was	
	spinal cord injury	developed with no	
	(26).	changes made to	
		the content (26).	
Goal Attainment-	The Goal	The GAS will be	(T1) (T3) (T4)
Goal Attainment	Attainment Scale is	provided to	
Scale (GAS) (27)	a method of	participants by the	
	scoring the level of	specified allied	
	achievement of a	health clinician at	
	participant's pre-	the timepoints	
	determined goal	noted. It will be	
	over the course of	administered in the	
	an intervention	form it was	
	(27).	developed and no	
		changes made to	
		the content, but	
		some formatting	
		changes made to	
		scoring table which	
		will be noted in	
		more detail in the	
		intervention	
		manual (27).	
		manuai (27).	

4 Study Treatments

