3.4 Flow of Study

An allied health clinician from the study site will collect demographic information such as age, gender, side of hemiparesis and time post stroke by asking the participant in an initial assessment and using the study demographic form (T1). In the same assessment (T1), the abilities of the participant using the Motor Assessment Scale for Stroke (MAS), Short Physical Performance Battery (SPPB), 2 Minute Walk Test (2MWT), Exercise Self Efficacy Scale (ESES) and the 12-Item Short Form Survey (SF-12) will be taken and recorded in the participant rehabilitation centre files (22-26). The clinician with the participant will then identify an 'area of difficulty' based on an individual activity limitation or participation. The clinician with the participant will establish one primary physical goal for the intervention and up to two secondary goals and score them based on the Goal Attainment Scale (GAS) (27). These outcomes and goals will be recorded the participant's rehabilitation centre files, handed over to treating therapists for the program and recorded in the participant's paper workbook.

Participants will then undergo the intervention and clinicians will record in their practice sheets the exercises completed and participant's perceived rating of exertion for each exercise for the duration

of the intensive program (via the Borg Rating of Perceived Exertion (RPE scale)) (28). After two weeks of the intensive program (T2), a summary of performance outcomes (SPPB and 2MWT) will be taken as an indicator of progress by an allied health clinician (23,24). These two outcome measures will be recorded in the participant's rehabilitation centre files and in a participant's paper workbook.

After the three-week intervention period (T3), an allied health clinician blinded to the preintervention outcome measures of the program will reassess the initial assessment measures (MAS,
SPPB, 2MWT and SF-12, ESES) and rescore the goals (using the GAS) (22-27). These outcomes, along
with the Borg perceived exertion ratings will be recorded in the participant's rehabilitation centre
files (28). Participants will also be given a post intervention survey by the allied health clinician to
determine the intervention's feasibility and effect on self-management and quality of life (this
survey is detailed below). This survey will be completed in allocated time outside the intervention

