either at home or in the clinic and if needed an allied health clinician or carer will be available to
support filling out the survey and collecting the surveys from participant. Completed surveys will be
filed in the participant's rehabilitation centre file and in a participant's paper workbook. Participants
will be followed up in three weeks (T4) by the same allied health clinician, who will complete a
follow up assessment to obtain follow up outcome measures (MAS, SPPB, 2MWT, ESES SF-12) and
participants will be asked to complete the same survey again under the same conditions and
provisional support as the first survey (22-26). The results from the survey and the outcome
measures will be filed in the participant's rehabilitation centre file.

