6.2 Data Analysis

De-identified data analysis will be conducted using SPSS Version 25. Demographic data will be

reported via descriptive statistics. Adherence data will be calculated from each week and from week 0 (T1) to week 3 (T2) and will be reported as mean repetitions per hour, session, and week and then as a percentage of overall sessions attended. Acceptability and self-management data will be taken from the surveys and will be reported as frequencies comparing time points week 3 (T3) and week 6 (T4). Acceptability data from the practice sheets use will be calculated from each week and from week 0 (T1) to week 3 (T3) and will be reported as mean values per week and then as a percentage overall. Paired t-tests will be used to analyse within group change over time for the clinical outcomes between week 0 (T1) to week 3 (T3) and between week 0 (T1) to week 6 (T4). Differences will be reported as a mean and 95% confidence interval.

7 Research Outcomes and Future Plans

Participants will have the opportunity to review their initial (T1) and post intervention (T3, T4) results with their treating allied health clinician (as per usual care at the study site). A publication and conference presentation are expected from this project to satisfy the requirement of the Master by Research candidature. Participants who have consented to participation in the research will be informed that only de-identified group data will be presented.

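### For MAS, SPPB, 2MWT and GAS the rater changes between baseline and T3/T4, so a consistent early-versus-late rater difference, if there is one, cannot be separated from the programme effect

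*Protocol*

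**What the plan says.** Protocol section 3.4 has the T1 measures taken by a site clinician: "An allied health clinician from the study site will collect demographic information", and the same assessment covers MAS, SPPB, 2MWT, ESES and SF-12 and sets the GAS goals. At T3, "an allied health clinician blinded to the preintervention outcome measures of the program will reassess the initial assessment measures" and rescore the goals. Participants then "will be followed up in three weeks (T4) by the same allied health clinician". Section 3.5.2 gives the same division: "This will be collected by an allied health clinician at timepoints (T1), (T2), and an allied health clinician blinded to the previous measures at timepoints"; the blinded assessments are those at T3 and T4.

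Section 6.2 reads "Paired t-tests will be used to analyse within group change over time for the clinical outcomes between week 0 (T1) to week 3 (T3" and goes on to name T1 to T4 as the second contrast. It adds: "Differences will be reported as a mean and 95% confidence interval". No T3-T4 test of the clinical outcomes is planned.

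Four other statements bear on the point:

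- Section 3.1 describes a single-group pre-post study at two sites.
- Section 2.4 makes an improvement in mobility of more than 10% the sign that the approach deserves further study.
- Table 1 requires MAS, SPPB and 2MWT to follow published standardised procedures, and describes the MAS as reliable between raters, without a coefficient. It makes no such statement for SPPB, 2MWT or GAS.
- Table 1 describes SF-12 and ESES as self-reported.

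**The concern.** In a single-group pre-post study, anything that changes systematically between the two assessments, other than the participant, enters the mean change. Here the person giving and scoring the tests changes at the same point as the programme takes place. Clinicians can differ in how strictly they score an item, how they instruct a walking test or how they judge whether a goal was met. A paired t-test sees only the sum of the programme effect and any such difference.

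At stake are the mean changes and confidence intervals for MAS, SPPB, 2MWT and GAS, and above all the 10% mobility indicator, which answers one of the protocol's two research questions. The shift could go in either direction, so it could create an apparent gain or hide a real one.

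**Working it through.** **Who rates when.** The passages compare as follows for the rater-administered outcomes.

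| Timepoint | Assessor as described | Consequence |
|---|---|---|
| T1 | a site clinician (3.4, 3.5.2) | takes the baseline scores |
| T2 (SPPB, 2MWT only) | a clinician, not said to be the same one | not in any planned test |
| T3 | blinded to pre-programme measures (3.4) | cannot be that participant's T1 rater |
| T4 | the T3 clinician (3.4) | not that participant's T1 rater either |

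The only continuity of rater that is stated is from T3 to T4, and that interval is not tested. Both tested intervals start at T1 and so cross the change of rater.

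**What the switch does.** Write the observed change for participant i as D_i = programme effect + r_i + error, where r_i is the late rater's scoring minus the early rater's scoring.

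- If the same people always rate early and others always late, r_i is a constant δ, and the mean of D estimates programme effect + δ.
- If r_i varies with mean zero, the mean of D is unaffected and the variance of D rises. The paired SD and the confidence interval already include that variance.

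The protocol does not say which case applies.

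**Illustrative size in the first case.** There is no figure in the plan to reproduce. The inputs are:

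- n = 15 (section 5.5, a recruitment estimate);
- a two-sided 5% level, matching the 95% interval in section 6.2;
- a true change of zero, and an offset δ in units of the SD of the change scores. Both are assumptions.

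The critical value is t(0.975, 14) = 2.145, so the half-width of the confidence interval is 2.145/√15 = 0.554 SD. The probability of a significant gain is P(T > 2.145), where T is noncentral t with 14 df and noncentrality δ√15.

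| Assumed δ (SD of change) | Noncentrality | P(significant gain) |
|---|---|---|
| 0 | 0 | 2.5% |
| 0.1 | 0.387 | 5.5% |
| 0.25 | 0.968 | 14.5% |
| 0.5 | 1.936 | 43.8% |

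**On the 10% indicator.** With an assumed constant offset of +2% or +5% of baseline, a true gain of 10 − 2 = 8% or 10 − 5 = 5% reads as 10%. With −2% or −5%, a true gain of 12% or 15% is needed to read as 10%.

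**Effect of counterbalancing.** Suppose two raters, with 8 participants assessed in one order and 7 in the other. The offset is then +δ for 8 and −δ for 7.

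- The residual shift in the mean is (8 − 7)δ/15 = δ/15, which is 0.033 SD at δ = 0.5.
- The SD of change becomes about √(1 + δ²): √1.0625 = 1.03 at δ = 0.25, and √1.25 = 1.12 at δ = 0.5.
- Simulation of this split with no true change gives a false-gain rate of 2.5% at δ = 0.25 and 2.0% at δ = 0.5.

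**The case against.** The strongest reply is that the switch is the price of a good decision. Blinding the post-programme assessor to baseline protects against expectation, and it necessarily means a different rater. The passages on the switch do not contradict one another. Mobility is secondary to feasibility, the tests follow standardised procedures, and the MAS is described as reliable between raters. The assumed offsets have no anchor in the documents, and the 10% indicator is not a significance test. Rotas and assessor identifiers are operational detail that a protocol for about 15 people might leave out.

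Much of this stands. It is a design trade-off and not an error in the text, the standardised procedures reduce the risk, and the percentages show only what an assumed offset would do.

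Three stronger readings also fail:

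- A reader might infer that every paired change is affected. SF-12 and ESES are self-reported, and the clinician only hands them out.
- A reader might infer that one named clinician does all baselines and another all later assessments, so that bias is certain. The wording is indefinite, there are two sites, and only the T3-to-T4 continuity is stated.
- A reader might count the lack of blinding at baseline as a fault. At T1 there is no earlier score to be blinded to.

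What does not stand is that blinding makes the problem unavoidable. It requires a different rater for each participant at T3/T4. It does not require the same people always to rate early and others always late. Nothing in the protocol prevents that split, and no rater calibration, double scoring or recording of assessor identity is described.

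**Conclusion.** The point holds in a limited, conditional form. It follows from the protocol's text that the rater of MAS, SPPB, 2MWT and GAS differs between T1 and T3/T4 within each participant, and that both planned contrasts cross that change. Whether this biases the mean or only widens the interval depends on how assessors are allocated, which the protocol leaves open. If the early and late raters are consistently different people, the single-group design offers no way to separate their difference from the programme effect.

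The size is unknown. The false-gain rates in the table rest on n = 15, no true change and assumed constant offsets, and should be read as a range and not as a forecast. The documents do not support saying that the reported changes will be biased, or in which direction. The matter is worth settling before recruitment because the order of assessors cannot be repaired once data are collected. It is a cheap improvement to the design, not a fault that undermines the primary feasibility aim.

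**What to change.** In sections 3.4 and 3.5.2, keep the blinding and add assessor counterbalancing within each site. For about half of the participants clinician A does the early assessments and clinician B the late ones; for the rest the order is reversed. State that no one assesses after the programme a participant whom they assessed at baseline, and that earlier scores are withheld from the T3/T4 assessor. The second statement matters because section 3.4 places those scores in the centre files and the participant's workbook. Record an assessor identifier at each timepoint.

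The cost is one data field and a rota, in which each clinician must be free for both early and late visits. No extra visits are needed. Extra staff are not needed if each site has two clinicians able to assess; the documents give no staffing numbers, so this is an assumption. Intervals become slightly wider because a fixed offset moves into the variance: the SD of change is about 12% larger at an offset of 0.5 SD, and about 3% larger at 0.25 SD.

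Any report of change by assessor order should be labelled descriptive, since with about 15 participants each order has only seven or eight. Where a site cannot rotate assessors, state the change of rater as a limitation of the mobility and GAS changes.

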4.1 Intervention

The participants will undergo the intensive program that was developed by the rehabilitation centre. The intervention is an intensive (45 hour over three weeks) therapy program delivered to a single group across two centres and provided on an 'intention to treat' basis and is described detail in the intervention manual. The intervention will be delivered by three disciplines (physiotherapy, exercise physiology and occupational therapy) working collaboratively to deliver the self-management program 'Take Charge', provide support in goal setting and deliver the strength, cardiorespiratory,

mobility and task specific therapy practice (19).

4.2 Resources

Minimal resources are required to conduct this project. All resources related to the delivery of the intervention will be provided by the research sites. Participants will be self-funding their attendance in the program as part of usual practice at the site.

5 Participant Enrollment

5.1 Recruitment

The recruitment of participants will occur over 6-month period from study commencement. As part of usual practice at the study site, clients elect to participate in an intensive multidisciplinary therapy program. The program is offered routinely in the clinic as an alternative to regular scheduled therapy and clients elect to participate in a 3-week intensive therapy program with the consent to the potential risks, costs and perceived benefit of the program. In the discussion with their elected therapist regarding the program, clients will be asked if they consent to be contacted by a member of the research team the understanding that any research conducted is additional to the program offered by the rehabilitation centre. Participants will be given 4-6 weeks to consider participation in the study.

5.2 Eligibility

The inclusion and exclusion criteria for the study are outlined below. Clients can participate in the program if:

- They are over 18 years of age
- Physical or Medical readiness to participate using the Physical Activity Readiness Questionnaire (PARQ) (29)
- They have sufficient mobility: They achieve 3 or more in the sitting component and 2 or more in the sitting to standing component of the Motor Assessment Scale for Stroke (MAS) (22).

5.3 Inclusion criteria

Participants will be included in the research study if:

- They have nominated to participate in an intensive mobility program at the study site and meet the sites criteria as listed above
- Have a primary diagnosis of stroke

5.4 Exclusion Criteria

Participants will be excluded from the research study:

- They cannot read or understand verbal or written English
- Do not have sufficient cognition to participate in a video guided or semi-supervised exercise program (as determined by their score on a Mini Mental State Examination (MMSE) > 24/30) (30).

5.5 Proposed Sample Size

An approximate sample size of fifteen people will be recruited to participate in this study. This is likely to be reflective of the size of population recruited from the intervention run by the two sites.

5.6 Informed Consent

If clients consent to being contacted to participate in the research, a rehabilitation staff member will provide a list of interested clients to the primary research investigator to be contacted via email, phone or in person. It will be made clear to the client that the decision to participate in the research is voluntary and will in no way affect their relationship or ongoing therapy with the rehabilitation centre. Investigators will provide the information and consent forms (PICF) to the clients who are interested and be available to contact should they have any questions regarding participation in the investigation. Clients who consent to participating in the research will be informed that data on their demographics, performance in the intensive program and responses to two surveys will be extracted from their client files and de-identified for group data analysis only. They will be informed that a follow up period of 3 weeks will be required after attending the intensive program as part of the research and they will need to be available for this extra time (a total of 7 weeks).

5.7 Withdrawal from the Study

Clients will be informed that they may choose to withdraw from the research at any time and it will in no way affect the intervention they continue to receive or their relationship with the rehabilitation center, and the result of their intervention will still be used to support their clinical care but will not be included in the data set. Screened participants who meet the research inclusion criteria and have consented to the collection of their data will be admitted for research data collection.

6 Data Management and Analysis

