3.2 Study Design

The study will look at the feasibility of providing this type of training offered to clients attending the program at the study sites. As part of the intensive program, participants will undertake 45 hours (three hours for five consecutive days over three weeks) of intensive, multidisciplinary practice both in the clinic and at home. At-home therapy will be delivered by video-guided exercise programs or individualised exercise programs. The primary outcome measure for this study will be feasibility, measured by adherence, acceptability, cost and safety. The secondary outcome measures for this study will be mobility, quality of life, self-efficacy skills and goal attainment. Outcome measures will be collected just prior commencement (week 0) (T1), midpoint (second week) (T2), upon completion of the intensive program (third week) (T3) and three weeks post intensive program (T4).

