3.5.1 Primary Outcome Measures

Feasibility of delivering the intervention will be in assessed using measures of adherence, acceptability, cost and safety. This will be collected by an allied health clinician at timepoints (T2), (T3) and (T4).

Adherence

Adherence will be measured by each participant in a workbook. The two measures of adherence will be percentage of sessions attended and number of repetitions completed per session will recorded in the participant's rehabilitation centre files. Attaining a personal best is encouraged in each session.

Acceptability

Acceptability will be determined via two methods, extracting perceived exertion (via the Borg Rating of Perceived Exertion (RPE scale)) from the practice sheets of participants at the study site at timepoints (T2), (T3) and (T4) and via purpose-built paper survey post intervention at timepoints (T3) and (T4) (28). The practice sheets will be stored on the participant's rehabilitation centre files. The paper survey will be provided in person by an allied health clinician from the study site. A paper survey was selected as in previous research at the study site there was a poor response to an electronic survey with participants requesting a paper-based survey. We expect the survey to take approximately 10 minutes to complete, participants will be given support to complete the study in clinic or may take the survey home to complete in time allocated outside the intervention. The

participant may receive support from a family member or carer. If requested, the allied health clinician may allocate time to assist in completion of the survey. Using a Likert scale, the survey will ask four questions:

- i) Were you satisfied with the program?
- ii) How easy was it to participate in the program?
- iii) Did the program give you adequate support?
- iv) Would you recommend the program?

They will also be given free text to input an answer to the following questions:

- i) What did you like or dislike about the multidisciplinary aspect of the program?
- ii) What did you like or dislike about the inclusion of Take Charge and participant workbook in the program?
- iii) What did you like or dislike about the amount of practice that was required?

Cost

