Cost will be reported by calculating the cost of the program per individual participant based on standard clinic fees. Participants will be charged for the therapeutic program as per usual care at the study site. Participants will not be charged for any research activities include assessments, surveys or research related follow up.

Safety

Safety will be monitored during training sessions by a member of the rehabilitation team and participants will be asked to log any events occurring at home in their participant workbook. All incidents will be recorded in the rehabilitation centre files and reported by the research team.

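### Section 5.7 drops every intervention result of anyone who withdraws from the research, including data collected before withdrawal, so the feasibility outcomes can be overstated and the promise to report all incidents is contradicted

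*Protocol*

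**What the plan says.** Section 5.7 tells clients that "they may choose to withdraw from the research at any time and it will in no way affect the intervention they continue to receive". For those who do so, "the result of their intervention will still be used to support their clinical care but will not be included in the data set". The section sets no cut-off date, so on its plain reading, data already collected go as well. Section 6.1 points the same way: the paper records are gathered for research once the intervention is over, and only for consenting participants. Section 6.2 has no rule that keeps, counts or describes people who withdrew.

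Section 3.2 sets the primary outcome: "The primary outcome measure for this study will be feasibility, measured by adherence, acceptability, cost and safety". On adherence, section 3.5.1 says: "The two measures of adherence will be percentage of sessions attended and number of repetitions completed per session". On safety it says: "All incidents will be recorded in the rehabilitation centre files and reported by the research team", with no exception for people who withdraw. Section 4.1 describes the intervention as "provided on an 'intention to treat' basis". On size, section 5.5 says: "An approximate sample size of fifteen people will be recruited to participate in this study". No withdrawal rate is given.

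**The concern.** In a feasibility study, who leaves, when and why is part of the answer. A rule that removes leavers and everything recorded about them takes that information out of the primary outcome and leaves a summary of those who stayed. If research withdrawal is more common among people who attend poorly, are dissatisfied or have an incident, the removal is selective and the remaining figures flatter the programme. With about 15 people, each removal takes 1/15 = 6.7% of the denominator, so a few are enough to move the result.

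For safety, one section promises complete reporting and another excludes a group's results. Neither says which governs an incident in someone who later withdraws.

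A later analysis plan could not easily repair this. The rule is fixed in the protocol, and clients are told of it.

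**Working it through.** **Plan's own figures.** The protocol states no dropout rate, power calculation or adherence threshold (section 2.5 expects only a high rate), so there is no figure to reproduce. The scheduled amount in section 3.2 is consistent: 3 hours × 5 days × 3 weeks = 45 hours, on 5 × 3 = 15 practice days.

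**Inputs.** From the protocol: N = 15 (section 5.5), and percentage of sessions attended as an adherence measure (section 3.5.1). Assumed: mean attendance a_c = 90% in those retained; a_w = 20%, 40%, 50% or 90% in those withdrawn; w = 1 to 5 withdrawals.

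**Adherence.** With everyone kept, the mean is [(15 − w)·a_c + w·a_w]/15. Under section 5.7 it is a_c. The overstatement is the difference, w·(a_c − a_w)/15. For example, with w = 3 and a_w = 40%, the full mean is (12 × 0.90 + 3 × 0.40)/15 = 80.0%, against 90% reported, which is 10.0 points too high.

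Overstatement in percentage points:

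| Withdrawn | a_w = 20% | a_w = 40% | a_w = 50% | a_w = 90% |
|---|---|---|---|---|
| 1 | 4.7 | 3.3 | 2.7 | 0 |
| 2 | 9.3 | 6.7 | 5.3 | 0 |
| 3 | 14.0 | 10.0 | 8.0 | 0 |
| 4 | 18.7 | 13.3 | 10.7 | 0 |
| 5 | 23.3 | 16.7 | 13.3 | 0 |

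The last column matters as much as the others: if those who leave the research attend as well as the rest, there is no bias.

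**How likely at least one withdrawal is.** With an assumed independent probability d per person, it is 1 − (1 − d)^15. This gives 54% for d = 5%, 79% for d = 10% and 96% for d = 20%.

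**Acceptability.** The survey is given only at T3 and T4, so the rule can delete survey answers only from someone who withdraws after T3. Exertion ratings are recorded throughout the programme and can be lost at any stage. Illustration: 3 people answer unfavourably at T3 and then withdraw, while the other 12 answer favourably. Deletion gives 12/12 = 100% (exact 95% CI 73.5% to 100%); keeping them gives 12/15 = 80% (51.9% to 95.7%).

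**Safety.** Suppose the one participant who withdraws had the only incident. If section 5.7 prevails, the report is 0/14 (upper exact 95% limit 23.2%). If section 3.5.1 prevails, it is 1/15 = 6.7% (0.2% to 31.9%). The text does not decide between them.

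**The case against.** The strongest reply is that section 5.7 concerns leaving the research, not leaving the programme. The programme is elected and self-funded; the research adds consent forms, surveys and a follow-up visit. A client who finds the training too much can stop it without revoking research consent, and nothing in section 5.7 removes that client. Conversely, someone may leave the research because of the surveys and still attend every session. This stands. A reader might infer that a programme which drives people out would necessarily look well attended, but that needs the further assumption that those who stop also withdraw research consent. This is plausible, since someone who stops has less reason to return for T3 and T4, but the protocol does not say it.

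Three other tempting readings also go too far:

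- **Intention to treat.** A reader might see a direct contradiction with section 4.1. There the phrase describes how the intervention is provided; it defines no analysis set. Deletion sits badly with the principle but breaks no stated analysis rule.
- **Safety.** A reader might infer that incidents will be under-reported. Section 3.5.1 promises the opposite, so what is shown is an unresolved contradiction.
- **Surveys and paired t-tests.** A reader might infer that early leavers' answers and pairs are deleted. Someone who leaves before T3 without further assessment has neither. The rule affects these only for withdrawals after T3, where it removes T3 data already obtained.

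It is also fair that removing data can be a participant's right when consent is withdrawn, and that nothing in section 5.7 forbids reporting how many withdrew. Neither point justifies making removal of data collected earlier the default for everyone.

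**Conclusion.** The point holds in this form: section 5.7 as written excludes all intervention results of anyone who withdraws from the research, with no limit to data after withdrawal. No other section cures this, and it contradicts the incident-reporting promise in section 3.5.1. Because feasibility is the primary outcome, adherence and acceptability will be overstated if research withdrawal is associated with poor attendance, dissatisfaction or an incident. That direction is likely but not certain.

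The range of about 3 to 23 points for adherence rests on assumed inputs: 15 starters, 90% attendance in those retained, 20–50% in those withdrawn, and 1 to 5 withdrawals. It falls to 0 under equal attendance. No figure in the protocol is wrong.

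**What to change.** Amend section 5.7 and the consent form as follows.

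1. Distinguish stopping the programme from withdrawing research consent.
2. Participants who stop the programme without withdrawing consent stay in the data set, and their remaining planned sessions count as not attended.
3. For those who withdraw from the research, keep data collected up to that date unless they ask for removal. Treat later sessions as unknown, or as not attended only if they also stopped the programme. Counting every later session as missed would record false non-attendance for clients who leave the research and keep attending, a case that section 5.7 expressly foresees.
4. Give a sensitivity range for the unknown sessions. For example, take 15 planned sessions (one per practice day), and one person who attended the first 5 and then left the research, with 14 others at 90%. Adherence lies between (14 × 0.90 + 5/15)/15 = 86.2% and (14 × 0.90 + 15/15)/15 = 90.7%.
5. Report the number, timing and, where given, reasons of all withdrawals, over all who started. Someone who asks for data removal is still counted as withdrawn.
6. Reconcile section 5.7 with section 3.5.1 so that incidents before withdrawal are reported, at least as de-identified counts where consent allows.

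The cost is a short wording change in two documents, an ethics amendment and possibly a less favourable adherence figure.
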